## 1) STUDY AIM, BACKGROUND, AND DESIGN ABSTRACT

This study aims to determine if application of Gebauer's Pain Ease or Gebauer's Ethyl Chloride numbing sprays will contaminate skin which has been prepped with chloraprep. Due to the recent national shortage of lidocaine we hope to be able to find a suitable alternative to lidocaine for topical analgesia during invasive procedures such as arterial lines and epidurals. Depending on the results of this study we will decide if it is safe to proceed to additional studies to determine if numbing sprays are effective alternatives to lidocaine for topical analgesia. Our plan is to compare the number of colony forming units (CFU) of bacteria that grow on a section of skin on the wrist and lower back prior to treatment, following chloraprep treatment, and following application of pain ease spray or ethyl chloride. Our hypothesis is that the sprays will not affect the sterility of the area and that there will not be a significant increase in bacterial growth after ethyl chloride or pain ease spray have been added to skin treated with chloraprep.

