#### 3) STUDY PROCEDURES

Our study will involve swabbing and culturing the skin of volunteers on the wrist where an arterial line is place, as well as on the lower back where an epidural is placed. First, a swab of the untreated area of wrist or lower back will be performed. Second, the section of skin will be treated with chloraprep according to standard procedure prior arterial line or epidural placement, and this treated skin will be swabbed. Third, the chloraprep-treated section of skin will be treated with numbing spray (either Gebaur's Ethyl Chloride or Pain Ease). For the Pain Ease group, the spray will be applied up to 10 seconds or until white appears (whichever comes first). If frosting appears, stop. The area that has been subsequently treated with chloraprep and numbing spray will then be swabbed. These swabs will be cultured by the HFHS microbiology lab on agar plates for 48 hours and the number of colony forming units (CFU) will be counted. The amount of bacterial growth will be compared between the untreated samples, chloraprep samples and the associated post-spray samples. Funding for the project will be from Gebauer, the manufacturer of the numbing sprays. Based on power analysis, for each spray, a sample size of 72 subjects with 6 swabs taken per subject (subsequent untreated, chloraprep, and numbing spray samples taken from the wrist and lower back from each subject) achieves 80 % power to detect an odds ratio of 24 using a two-sided McNemar test with a significance level of 0.05. The odds ratio is equivalent to a difference between two paired proportions of 0.115 which occurs when the proportion in cell 1,2 is 0.12 and the proportion in cell 2,1 is 0.005. The proportion of discordant pairs is 0.125. As there are two separate sprays being investigated independently, the final number of subjects will be 144, with 6 swabs taken per subject.

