## **Data Analysis and Statistical Considerations**

We will collect data on an excel spreadsheet. We will not collect any personal health information or identifying information for the participants.

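### Must the plan say which unit the 0.115 difference refers to, and what a spray's result is when wrist and lower back disagree?

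*Combined protocol and SAP*

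**What the plan says.** Section 3 (Study procedures) takes swabs "on the wrist where an arterial line is place, as well as on the lower back where an epidural is placed". For each spray it plans "a sample size of 72 subjects with 6 swabs taken per subject", the six being "untreated, chloraprep, and numbing spray samples taken from the wrist and lower back from each subject". The power statement is for a two-sided McNemar test at 0.05 with 80% power. Its effect is "a difference between two paired proportions of 0.115 which occurs when the proportion in cell 1,2 is 0.12", with 0.005 in the opposite cell, an odds ratio of 24 and 0.125 discordant. The total of 144 subjects follows from "two separate sprays being investigated independently".

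The same section says that growth in the chloraprep samples will be compared with growth in the post-spray samples associated with them. Section 1 gives the purpose: "Our hypothesis is that the sprays will not affect the sterility of the area", and depending on the results "we will decide if it is safe to proceed to additional studies". The section headed Data Analysis and Statistical Considerations covers data capture and privacy only ("We will collect data on an excel spreadsheet"). No section says in so many words whether the two sites are tested separately or combined.

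**The concern.** A McNemar test needs a defined binary pair. Each volunteer supplies two chloraprep/post-spray pairs, so a spray has 2 × 72 = 144 pairs, while the power statement uses 72. Two things then look open.

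- **The detectable effect.** If 0.12 and 0.005 describe one site, the design detects an 11.5-point increase at that site. If they describe a volunteer who counts as positive when either site grows, the same figures imply a smaller increase at each site.
- **The conclusion.** The hypothesis is worded for the sprays as a whole. Nothing says what is concluded if the wrist shows a significant increase and the lower back does not.

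The result informs whether further studies are safe, and the hoped-for finding is no significant increase. If the unit were chosen after the counts were seen, the same data might be described as contamination or as no significant increase.

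**Working it through.** **1. Inputs (section 3).** n = 72 subjects per spray; p12 = 0.12; p21 = 0.005; two-sided alpha 0.05. The figures agree with each other: 0.12/0.005 = 24; d = 0.12 − 0.005 = 0.115; pd = 0.12 + 0.005 = 0.125.

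**2. The stated power.** The usual paired formula is power = Φ[(d√n − 1.96√pd) / √(pd − d²)].

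- d√n = 0.115 × 8.485 = 0.976
- 1.96√pd = 1.96 × 0.3536 = 0.693
- √(pd − d²) = √(0.125 − 0.0132) = 0.334
- Power = Φ(0.283/0.334) = Φ(0.846) = 0.801

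The same formula solved for n gives 71.8, so 72. Enumerating all outcomes at 72 pairs gives 0.789 for the exact test and 0.899 for the uncorrected chi-square. With 144 pairs treated as independent, the formula would give 0.980. The stated 80% therefore counts one pair per volunteer and does not treat the two sites as extra independent subjects.

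**3. Which pair the text supports.** Three features of section 3 agree. The chloraprep sample is compared with its associated post-spray sample, which ties a sample to its own counterpart at the same site. Each site is introduced by its own procedure, arterial line or epidural. And n = 72 is the number of pairs available at each site. No section describes a volunteer-level result such as growth at either site.

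**4. How often the sites would disagree on that reading.** Take the planned effect to be true at both sites and the sites to be independent. With power s at each site, the chances are s² (both significant), 2s(1 − s) (exactly one) and (1 − s)² (neither).

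| Power per site | Both | Exactly one | Neither |
|---|---|---|---|
| 0.80 (stated) | 64% | 32% | 4% |
| 0.789 (exact) | 62% | 33% | 4.4% |
| 0.899 (uncorrected) | 81% | 18% | 1% |

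The within-person correlation is not in the documents. It was varied by simulation (60,000 runs, the second site copying the first with probability 0.13, 0.3 or 0.5). Exactly one site is then significant in 31%, 28% and 23% of comparisons (exact), or 17%, 16% and 13% (uncorrected). With full dependence it is 0%.

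**5. The either-site reading, for illustration only.** Suppose a volunteer is positive when either site grows, the sites are equal and independent, and 0 to 5% of pairs grow on both swabs. None of this is in the documents. Let a and b be the per-site discordant proportions and p00 the proportion with no growth on either swab. Solve (p00 + a)² − p00² = 0.12 and (p00 + b)² − p00² = 0.005. The per-site increase is 5.9 to 6.3 points; if the same volunteers change at both sites, it rises to as much as 11.5. Power at one site for the 5.9 to 6.3 points is 25–29% exact, 51–53% by the formula in step 2, and 57–61% uncorrected. Much of that spread comes from the McNemar variant, not from the choice of unit.

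**6. What another rule would buy (exact test throughout).**

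- Small increase shared by both sites, as in step 5 with no pair growing on both swabs: 25% at each site against 79% for the volunteer-level result.
- Effect at one site only (0.12/0.005 there, 0.005/0.005 at the other): 79% for that site against 70–74% for the volunteer-level result.
- False alarms in the direction of increase, 12.5% discordance, independent sites: about 1.0% at one site against about 2.0% if either site may trigger (uncorrected, 2.2% and 4.3%).

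No rule is better in every case.

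**The case for a change.** The strongest case for a change is that the result feeds a safety decision, the wording is silent, and two sentences would close the gap at no cost in volunteers or swabs. Because 72 is both the number of volunteers and the number of pairs per site, the arithmetic alone cannot separate a per-site from a volunteer-level reading. Even if the sites are tested separately, section 1 asks about the sprays as a whole, and a split result at the planned effect is a realistic outcome.

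The silence is real, and so is the chance of a split. But section 1 describes a judgement made in the light of the results, not a formal pass/fail rule needing one answer per spray. A split reported by site is informative for that judgement, since wrist and lower back serve different procedures. The claim that a unit would be picked after the counts are seen is a possibility, not something the plan provides for. One caution stands: anyone who pools the 144 pairs must allow for two pairs from the same volunteer. The plan does not propose pooling, and its sample size does not rely on it.

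**Conclusion.** No change follows. This is a gap in wording that a competent analyst fills from the text: one chloraprep/post-spray pair per volunteer at each site, tested and reported by site, with 0.12/0.005 and 80% taken per site. On that reading every stated number stands (80.1% by formula, 78.9% exact, at 72 pairs).

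If the planned effect is present at both sites, exactly one would reach significance in 18% (uncorrected) to 33% (exact) of comparisons for independent sites, less with correlation and never with full dependence. With independent sites, both would miss in only about 1% to 4.4%, so an increase of the planned size would usually show at one site or the other provided both are reported. The smaller per-site effects of an either-site reading rest on a construct that the plan does not contain. A single combined rule per spray would gain sensitivity in some situations and lose it in others.

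The conclusion assumes that the pair is chloraprep versus post-spray, as the hypothesis in section 1 implies, and that both sites are reported whatever they show.

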## **Data Analysis and Statistical Considerations**

We will collect data on an excel spreadsheet. We will not collect any personal health information or identifying information for the participants.

#### 4) ANTICIPATED RISKS

There are no likely risks to participants in this study. Less likely risks include hypersensitivity to the products, risk of frostbite, risk of skin pigment alteration, and Ethyl Chloride is a flammable substance. We will decrease the risk of frostbite by limiting exposure to the numbing sprays to the initial formation of crystals on the skin.

#### 5) ANTICIPATED BENEFITS

There are no anticipated benefits to the participants however we hope that this study will allow us to perform additional trials which may benefit others.

## 6) RENUMERATION/COMPENSATION

There will be no compensation offered to participants.

## 7) COSTS

The only costs associated with this project will be the materials used. The manufacturer of pain ease and ethyl chlorides sprays will cover the costs of these products.

## 8) ALTERNATIVES

There are no alternatives

## 9) CONSENT PROCESS AND DOCUMENTATION

Consent of volunteers will be obtained by one of the investigators prior to participation in the study. Participants will be given written consent and offered the opportunity to ask any questions they may have prior to participation in the study. Consent forms will be signed and stored in the primary investigators locked office.

## 10) WITHDRAWAL OF SUBJECTS

There are no anticipated circumstances under which subjects will be withdrawn from research without their consent.

### 11) PRIVACY AND CONFIDENTIALITY

No personal identifiers will be kept or obtained for participants in the study. We will not be accessing the health records of patients.

### 12) DATA AND SAFETY MONITORING PLAN

Data quality will be maintained by the primary investigator as well as the co-investigators.

